## COMMENTS REGARDING THE USE OF THESE TABLES

- Standardized and commonly used toxicity tables (Division of AIDS, National Cancer Institute [NCI] Common Toxicity Criteria [CTC], and World Health Organization [WHO]) have been adapted for use by the Division of Microbiology and Infectious Diseases (DMID) and modified to better meet the needs of participants in DMID trials.
- For parameters not included in the following Toxicity Tables, DEPRU should refer to the "Guide for Estimating Severity Grade" located above.
- Criteria are generally grouped by body system.
- Some protocols may have additional protocol specific grading criteria, which will supersede the • use of these tables for specified criteria.

Clinical Adverse Events				
VITAL SIGNS	Mild (Grade 1)	Moderate (Grade 2)	Severe (Grade 3)	
Fever (°C) *	38.0 - 38.4	38.5 - 38.9	≥39.0	* Oral temperature; no recent hot or cold beverages or smoking.
(°F) *	100.4 - 101.1	101.2 - 102.0	≥102.1	
Tachycardia - beats per minute	101 – 115 and >25% change from baseline	116 – 130 and >25% change from baseline	
 
> 130 or
 
ventricular
 
dysrhythmias and
 
>25% change
 
from baseline
 
	

## Table 10: Clinical adverse event definition and grading scale

## DMID/NIAID/NIH

IV Fosfomycin PK Study

Bradycardia - beats per minute	50 – 54 or 45 - 49 bpm if baseline <60 bpm - Subject is asymptomatic; no treatment required 141-150	45 – 49 or 40 - 44 if baseline <60 bpm - Subject is asymptomatic; no treatment required; Site PI/sub- investigator may confirm with ECG or 12-lead Holter monitors to rule out arrhythmia or advanced heart block. 151-160	< 45 or <40 bpm if baseline <60 bpm - Subject is symptomatic and/or requires treatment; Site PI/sub- investigator should confirm with ECG or 12- lead Holter monitors to rule out arrhythmia or advanced heart block > 160	Assuming supine position, 10 min at rest conditions, not sleeping subjects measurements on the same arm and several concordant results.
Hypertension (diastolic) - mm Hg	91-95	96-100	> 100	
Hypotension (systolic) - mm Hg	85-89	80-84	< 80	
Tachypnea – breaths per minute	23-25	26-30	>30	
CARDIOVASCULAR	Grade 1	Grade 2	Grade 3	

## DMID/NIAID/NIH

## IV Fosfomycin PK Study

Hemorrhage, Blood Loss	Estimated blood loss < 100 mL	Estimated blood loss > 100 mL, no transfusion required	Transfusion required	
QTc interval (prolonged)	QTc 450-480 msec	QTc 481-500 msec	QTc >500 msec	
PR Interval (prolonged)	PR 200-250 msec and >25% change from baseline	PR >250 msec and >25% change from baseline	AV block 2 nd degree Type II or higher OR ventricular pause >3 sec	
QRS Interval (prolonged)	QRS 120-150 msec and >25% change from baseline	QRS 150-180 msec and >25% change from baseline	New bundle branch block	
RESPIRATORY	Grade 1	Grade 2	Grade 3	
Cough	Transient- no treatment	Persistent cough;	Interferes with daily activities	
Bronchospasm, Acute	Transient; no treatment; 71% - 80% FEV1 of peak flow	Requires treatment; normalizes with bronchodilator; FEV1 60% - 70% (of peak flow)	No normalization with bronchodilator; FEV1 <60% of peak flow	
Dyspnea	Does not interfere with usual and social activities	Interferes with usual and social activities, no treatment	Prevents daily and usual social activity or requires treatment	
GASTROINTESTINAL	Grade 1	Grade 2	Grade 3	
Nausea	No interference with activity	Some interference with activity	Prevents daily activities	

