9.8. ECG Assessments

An ECG will be performed at Screening, Baseline and within 1-2 hours of the last dose (3rd dose) of study drug and include the following parameters: QTc Interval, PR Interval, and QRS Duration. The grading scale for ECG evaluations is included in Table 4.

ECG change in overall interpretation from Baseline to Post Dose 3 will be shown in Table 30. Summaries of ECG results by severity for each parameter will be tabulated by timepoint and presented in Table 31.

Summary statistics of ECG results including mean, SD, median, min and max values by timepoint and change from baseline for the Post Dose 3 timepoint will be tabulated and presented by parameter for baseline and each post dose timepoint (Table 32). Data will be visualized using box plots showing the change from baseline at post Dose 3 (Figure 43, Figure 44, Figure 45).

Individual data listings of ECG results will be presented (Listing 17).

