URINE Protein	Mild (Grade 1) 1+	Moderate (Grade 2) 2+	Severe (Grade 3) >2+
URINE Protein Glucose	Mild (Grade 1) 1+ 1+	Moderate (Grade 2) 2+ 2+ 2+	Severe (Grade 3) >2+ >2+

cale
2

Clinical Adverse Events				
VITAL SIGNS	Mild (Grade 1)	Moderate (Grade 2)	Severe (Grade 3)	
Fever (°C) *	38.0 - 38.4	38.5 - 38.9	≥39.0	* Oral temperature; no recent hot or cold beverages or smoking.
(°F) *	100.4 - 101.1	101.2 - 102.0	≥102.1	
Tachycardia - beats per minute	101 – 115 and >25% change from baseline	116 – 130 and >25% change from baseline	> 130 or ventricular dysrhythmias and >25% change from baseline	
Bradycardia - beats per minute	50 – 54 or 45 - 49 bpm if baseline <60 bpm - Subject is asymptomatic; no treatment required	45 – 49 or 40 -44 if baseline <60 bpm - Subject is asymptomatic; no treatment required; Site PI/sub-investigator may confirm with ECG or 12-lead Holter monitors to rule out arrhythmia or advanced heart block.	< 45 or <40 bpm if baseline <60 bpm - Subject is symptomatic and/or requires treatment; Site PI/sub- investigator should confirm with ECG or 12-lead Holter monitors to rule out arrhythmia or advanced heart block	
Hypertension (systolic)- mm Hg	141-150	151-160	> 160	Assuming supine position, 10 min at rest conditions, not sleeping subjects measurements on the same arm and several concordant results.
Hypertension (diastolic) - mm Hg	91-95	96-100	> 100	
Hypotension (systolic) - mm Hg	85-89	80-84	< 80	
Tachypnea – breaths per minute	23-25	26-30	>30	
CARDIOVASCULAR	Grade 1	Grade 2	Grade 3	
Hemorrhage, Blood Loss	Estimated blood loss \leq 100 mL	Estimated blood loss > 100 mL, no transfusion required	Transfusion required	
QTc interval (prolonged)	QTc 450-480 msec	QTc 481-500 msec	QTc >500 msec	
PR Interval (prolonged)	PR 200-250 msec and >25% change from baseline	PR >250 msec and >25% change from baseline	AV block 2 nd degree Type II or higher OR ventricular pause >3 sec	
QRS Interval (prolonged)	QRS 120-150 msec and >25% change from baseline	QRS 150-180 msec and >25% change from baseline	New bundle branch block	
RESPIRATORY	Grade 1	Grade 2	Grade 3	
Cough	Transient- no treatment	Persistent cough;	Interferes with daily activities	
Bronchospasm, Acute	Transient; no treatment; 71% - 80% FEV1 of peak flow	Requires treatment; normalizes with bronchodilator; FEV1	No normalization with bronchodilator; FEV1 <60% of peak flow	

Clinical Adverse Events				
		60% - 70% (of peak flow)		

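### The QRS grading scale gives 150 ms two grades and values above 180 ms none, and SAP Table 31 names no source for Grade 3 PR or QRS

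*Protocol*

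**What the plan says.** Appendix B of the protocol (Table 10) and SAP Table 4 carry the same ECG grading rows.

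- **QRS.** Grade 1 is "QRS 120-150 msec and >25% change from baseline", Grade 2 is "QRS 150-180 msec and >25% change from baseline" and Grade 3 is "New bundle branch block".
- **PR.** Grade 1 is "PR 200-250 msec and >25% change from baseline" and Grade 2 is "PR >250 msec and >25% change from baseline". Grade 3 is AV block of second "degree Type II or higher OR ventricular pause >3 sec".
- **QTc.** All three grades are millisecond bands: 450-480, 481-500 and over 500.

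SAP 9.8 says that the ECGs "include the following parameters: QTc Interval, PR Interval, and QRS Duration", and that Table 4 supplies the grading scale. It continues: "Summaries of ECG results by severity for each parameter will be tabulated by timepoint and presented in Table 31". The Table 31 shell has a block for each parameter, with columns for None, Grades 1 to 3 and Missing.

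The only other ECG data in the SAP are an overall interpretation (Table 30: normal, abnormal but not clinically significant, abnormal and clinically significant) and an overall assessment column in Listing 17 whose content is not described. Under Protocol 8.1 the investigator reads every ECG, and Day 2 abnormalities are handled by Appendix B.

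**The concern.** A severity scale should give each result exactly one grade, and a worse result should not receive a lower one. The QRS row fails on both counts. The bands meet at 150 ms without saying which one owns it. They stop at 180 ms, where the criterion changes from a width to a diagnosis.

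The second problem concerns the table. Its Grade 3 columns for PR and QRS need findings that are not interval values, and the SAP does not say where those findings come from. Nor does it say what Table 31 shows when the finding and the interval band disagree. ECGs belong to the stated safety outcome (Protocol 3.2), so a zero in a Grade 3 cell invites the reading that no severe conduction event occurred.

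**Working it through.** The plan gives no figure to reproduce here. The check applies the printed rules to whole-millisecond values, with change = (value − baseline) / baseline.

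**1. Overlap at 150 ms.** Both bands include 150, and both need a change above 25%.
- The change exceeds 25% when 150 / baseline > 1.25, that is, when baseline < 150 / 1.25 = 120 ms.
- Baseline 119 ms: 150 / 119 = 1.261, so Grades 1 and 2 both apply.
- Baseline 120 ms: 150 / 120 = 1.250, which is not above 25%, so neither applies.
- For the baselines tried from 80 to 143 ms, 150 ms was the only value with two grades.

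**2. Gap above 180 ms.** Take a baseline of 100 ms and no new bundle branch block.
- QRS 170 ms: change 70 / 100 = 70%, Grade 2.
- QRS 190 ms: change 90 / 100 = 90%, no grade.
- Every value tried from 181 to 260 ms had the required change and no grade.

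The general severity guide in Appendix B does not fill the gap, because it is limited to abnormalities that the tables do not list. QRS prolongation is listed.

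**3. PR bands.** With baselines from 120 to 199 ms, no PR value had two grades. No PR of 200 ms or more with over 25% change was ungraded, because Grade 2 has no upper limit. PR Grades 1 and 2 can be applied as written.

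**4. Grade 3 from the interval alone.**

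| Parameter | Grade 3 criterion | Reachable from the interval? |
|---|---|---|
| QTc | over 500 ms | yes |
| PR | AV block or ventricular pause | no |
| QRS | new bundle branch block | no |

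**5. Disagreement between interval and finding.** A QRS rising from 95 to 140 ms with a new bundle branch block has 140 / 95 = 1.47, a 47% change. It is Grade 1 by width and Grade 3 by finding. SAP 9.8 and Table 31 do not say which grade the timepoint row shows.

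**6. Baseline row.** At baseline the change is zero by definition, so PR and QRS Grades 1 and 2 cannot occur in that row of Table 31.

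**The case against.** **A reader might infer that the Grade 3 PR and QRS cells are bound to be zero whatever happens.** The documents do not support that. It holds only if Table 31 is programmed from the three intervals alone, which the SAP does not say. The scale that the SAP cites names the diagnoses, the investigator reads each ECG, and clinicians grade AEs on the same scale (Protocol 9.2.1). The overall assessment field in Listing 17 might hold a diagnosis. The eCRF is not among the documents. What stands is that no source is specified.

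**A reader might also infer that the PR grading fails as a whole.** It does not: step 3 shows that PR Grades 1 and 2 are sound.

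**Other outputs limit the harm.** Table 30 shows shifts in overall interpretation. Table 32 prints the maximum QRS and PR, and Listing 17 gives individual values, so a 190 ms QRS would still be visible. A block recorded as an AE would appear in the AE tables, where subjects are counted at their most severe grade (Protocol 11.3, SAP 9.3). The halting rules in Protocol 9.5 use related Grade 3 AEs, not Table 31. All of this stands. It does not repair the scale, which the investigator also uses on Day 2.

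**The events should be rare.** Subjects are healthy adults, clinically significant screening ECG abnormalities are excluded (Protocol 5.2), and Protocol 2.1 reports no abnormal ECG intervals in the earlier healthy-volunteer study. Protocol Table 8 cannot size the problem, because it gives the chance of seeing any event at an assumed rate, not the chance of a misgraded ECG. This also stands, and keeps the point minor.

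**A very wide QRS might always come with a new bundle branch block**, which would close the gap in practice. The documents do not say so.

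**Conclusion.** The QRS rule is wrong as written in both documents. It assigns two grades at 150 ms when baseline is below 120 ms, and none above 180 ms when the change exceeds 25% and there is no new bundle branch block. If Table 31 follows the scale literally, such a QRS could be counted under None while a narrower one is Grade 2.

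The lack of a stated source and precedence for Grade 3 PR and QRS is a separate gap in specification. Until a source is named, a zero in those cells cannot be taken as evidence of no event. Whether the dataset already holds a suitable field cannot be judged from these documents.

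The expected numerical effect is small. The documents give no rate for wide QRS or conduction block from which to put a figure on it. This is a low-priority correction to a safety display and its grading scale. It does not touch the pharmacokinetic analyses.

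**What to change.** 1. **Protocol Table 10 and SAP Table 4.** The sponsor reconciles the QRS bands, identically in both, so that every value has exactly one grade, including 150 ms and values above 180 ms. Which grade each receives is for the sponsor to decide.
2. **SAP 9.8 and Table 31.** Name the source of Grade 3 PR and QRS, either the investigator's ECG interpretation or a linked AE record, and state that the highest applicable grade is shown. If no such field exists, mark those cells as not derivable instead of zero and refer the reader to the AE tables.
3. **Table 31 footnote.** State that PR and QRS Grades 1 and 2 cannot occur in the Baseline row because they require more than 25% change from baseline.

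The cost is a few table cells in each document, a sentence or two in SAP 9.8 and a footnote. If the ECG finding is not already in the dataset, one further variable has to be carried.

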## DMID/NIAID/NIH

## IV Fosfomycin PK Study

	•	•	•	
Vomiting	No interference with activity or 1 - 2 episodes/24 hours	Some interference with activity or > 2 episodes/24 hours	Prevents daily activity or requires IV hydration	
Diarrhea	2 - 3 loose or watery stools or < 400 gm/24 hours	4 - 5 loose or watery stools or 400 - 800 gm/24 hours	6 or more loose or watery stools or > 800gms/24 hours or requires IV hydration	
REACTOGENICITY				
LOCAL REACTIONS	Grade 1	Grade 2	Grade 3	
Pain	Does not interfere with activity	Repeated use of non-narcotic pain reliever > 24 hours or interferes with activity	Any use of narcotic pain reliever or prevents daily activity	
Tenderness	Discomfort only to touch	Discomfort with movement	Significant discomfort at rest	
Erythema/Redness **	2.5 - 5 cm	5.1 - 10 cm	> 10 cm	** In addition to grading the measured local reaction at the greatest single diameter, the measurement should be recorded as a continuous variable.
Induration/Swelling ***	2.5 - 5 cm and does not interfere with activity	5.1 - 10 cm or interferes with activity	> 10 cm or prevents daily activity	***Induration/S welling should be evaluated and graded using the functional scale as well as the

## DMID/NIAID/NIH

IV Fosfomycin PK Study

27 August 2020

	r		1	
				actual measurement
SYSTEMIC	Grade 1	Grade 2	Grade 3	
Allergic Reaction	pruritus without rash	localized urticaria	generalized urticaria; angioedema or anaphylaxis	
Headache	No interference with activity	Repeated use of non-narcotic pain reliever > 24 hours or some interference with activity	Significant; any use of narcotic pain reliever or prevents daily activity	
Fatigue	No interference with activity	Some interference with activity	Significant; prevents daily activity	
Myalgia	No interference with activity	Some interference with activity	Significant; prevents daily activity	
ALL OTHER CONDITIONS	Grade 1	Grade 2	Grade 3	
Illness or clinical adverse event (as defined according to applicable regulations)	No interference with activity	Some interference with activity not requiring medical intervention	Prevents daily activity and requires medical intervention	

DMID/NIAID/NIH

LABORATORY ADVERSE EVENTS			
BLOOD, SERUM, PLASMA	Mild (Grade 1)	Moderate (Grade 2)	Severe (Grade 3)
Sodium – Hyponatremia mEq/L	132 - <lln< td="">130 - <132	<130	</lln<>	130 - <132	<130
Sodium – Hypernatremia mEq/L	>ULN - 148	>148-150	>150
Potassium – Hyperkalemia mEq/L	>ULN - 5.2	>5.2 - 5.4	>5.4
Potassium – Hypokalemia mEq/L	3.1- <lln< td="">3.0-<3.1	<3.0	</lln<>	3.0-<3.1	<3.0
Glucose – Hypoglycemia mg/dL	65 - 69	55 - <65	<55
Glucose – Hyperglycemia Fasting – mg/dL	>ULN - 120	>120 - 130	>130
Glucose – Hyperglycemia Random – mg/dL	141 - 159	>159-200	>200
Blood Urea Nitrogen mg/dL	21-26	>26-31	> 31
Creatinine – mg/dL	>ULN - 1.7	>1.7 - 2.0	>2.0
Calcium – hypocalcemia mg/dL	8.0 - <lln< td="">7.5 - < 8.0	<7.5	</lln<>	7.5 - < 8.0	<7.5
Calcium – hypercalcemia mg/dL	>ULN - 11.0	>11.0 - 11.5	>11.5
Magnesium – hypomagnesemia mg/dL	1.3 – 1.7	1.1 - <1.3	<1.1
Phosphorous – hypophosphatemia mg/dL	2.1 – 2.2	1.9 - <2.1	<1.9
CPK – mg/dL	221-1000	>1000-1500	>1500
Albumin – Hypoalbuminemia g/dL	2.8-3.4	2.5 - <2.8	< 2.5
Total Protein – Hypoproteinemia g/dL	5.2 – <lln< td="">5.0 - < 5.2	< 5.0	</lln<>	5.0 - < 5.2	< 5.0
Alkaline phosphatase (ALP) – U/L	111 - 240	>240-360	>360
AST U/L	42 - 105	>105-175	>175
ALT U/L (Female)	>ULN - 105	>105-175	>175
ALT U/L (Male)	>ULN - 105	>105-175	>175
Bilirubin (serum total) - mg/dL	1.6 - 2.5	>2.5 - 3.0	> 3.0
Direct bilirubin – mg/dL	0.7-2.0	>2.0-3.5	>3.5
Total cholesterol – mg/dL	301 - 400	>400-500	>500
Triglycerides – mg/dL	>500 - 750	>750 - 1000	>1000
Lactate dehydrogenase – U/L	>200-500	>500-800	>800
Hemoglobin (Female) - g/dL	11.0 - 11.9	9.5 - <11.0	< 9.5

## Table 11: Laboratory adverse event definition and grading scale

#### DMID/NIAID/NIH

CONFIDENTIAL

IV Fosfomycin PK Study

27 August 2020

Hemoglobin (Male) - g/dL	12.0 - 13.6	10.0-<12.0	<10.0
WBC Increase - cell/mm3	9900 - 15,000	>15,000 - 20,000	> 20,000
WBC Decrease - cell/mm3	2,500 - 3100	1,500-<2,500	< 1500
Lymphocytes Decrease - cell/mm3	500 - <600	400 - <500	< 400
Neutrophils Decrease - cell/mm3	1,500 - < 2000	1000 - <1500	< 1000
Eosinophils - cell/mm3	> 700 - 750	>750 - 1500	> 1500
Platelets Decreased - cell/mm3	120,000 - < 149,000	100,000 - <120,000	<100,000
PT – seconds (prothrombin time)	> ULN - 14.4	>14.4 - 15.7	> 15.7
aPTT – seconds (activated partial	> ULN - 42.1	>42.1 - 50.0	> 50.0
thromboplastin time)			
URINE	Mild	Moderate	Severe
	(Grade 1)	(Grade 2)	(Grade 3)
Protein	1+	2+	>2+
Glucose	1+	2+	>2+
Blood (microscopic) - red blood cells per	5-10*	>10-50*	> 50 and/or
high power field (rbc/hpf)			gross
			blood*

\* Isolated presence of blood in urinalysis is acceptable for menstruating females.

DMID/NIAID/NIH

# **APPENDIX C: VENIPUNCTURE SCHEDULE AND VOLUMES**

Scheduled Laboratory Assessments	Study Days			Blood Volume per Sample (mL)	Total Number of Samples	Total Blood Volume (mL)
	Screening (Day -30 to Day -1)	Baseline (Day -1 to Day 1)	Treatment and Discharge (Days 1-2)			
Chemistry	X	Х	Х	9	3	27
Electrolytes (only)			Х	4.5	1	4.5
Hematology	Х		Х	4	2	8
Coagulation	X		Х	2.7	2	5.4
Serum Pregnancy	X			5	1	5
Serology a	X			8.5	1	8.5
Urea Blood Sample			X	4	1	4
PK Blood Samples			Х	4	15	60
Total blood volume (mL) b	29.2	9	84.2			122.4

## Table 12: Venipuncture schedule and volumes

a Serology is for testing of HIV antibody, Hepatitis B antigen, Hepatitis C antibody.

b The total blood volume of 122.4 ml will be collected from each subject; blood volume per study phase is reflected at the bottom of each column.

DMID/NIAID/NIH

BUN	Blood Urea Nitrogen
С	Degree(S) Celsius
CI	Confidence Interval
C _{max}	Maximum Measured Plasma Concentration
СРК	Creatine Phosphokinase
CRF	Case Report Form
CSR	Clinical Study Report
CV	Coefficient Of Variation
DCC	Data Coordinating Center
DMID	Division Of Microbiology And Infectious Diseases
DSMB	Data And Safety Monitoring Board
ECG	Electrocardiogram
ELF	Epithelial Lining Fluid
GM	Geometric Mean

LIST OF ABBREVIATIONS

List of Abbre	eviations (continued)
GSD	Geometric SD
h	Hour(S)
hCG	Human Chorionic Gonadotropin
HCV	Hepatitis C Virus
HIV	Human Immunodeficiency Virus
ICH	International Conference On Harmonisation
IRB	Institutional Review Board
ISM	Independent Safety Monitor
IV	Intravenous
L	Liter
LDH	Lactate Dehydrogenase
LLN	Lower Limit Of Normal
LLOQ	Lower Limit Of Quantification
max	Maximum
mcg	Microgram
MedDRA	Medical Dictionary For Regulatory Activities
mEq	Milliequivalent
mg	Milligram
MH	Medical History
min	Minimum
mL	Milliliter
МОР	Manual Of Procedures
Ν	Number (Typically Refers To Subjects)
NCA	Noncompartmental Analysis
NIH	National Institutes Of Health
PI	Principal Investigator
РК	Pharmacokinetics
РТ	Prothrombin Time
RBC	Red Blood Cell
RCD	Reverse Cumulative Distribution
RV	Residual Variability

List of Abbreviations (continued)	
SAE	Serious Adverse Event
SAP	Statistical Analysis Plan
SD	Standard Deviation
SDCC	Statistical And Data Coordinating Center
SDTM	Standard Data Tabulation Model
SMC	Safety Monitoring Committee
SOC	System Organ Class
SOP	Standard Operating Procedures
t _{1/2}	Terminal Elimination Half-Life
TEAE	Treatment Emergent Adverse Event
TFLs	Tables, Figures, And Listings
t _{max}	Time To Peak Concentration
U	Units
ULN	Upper Limit Of Normal
V _d	Volume Of Distribution
VPC	Visual Predictive Checks
WBC	White Blood Cell
WHO	World Health Organization
λ_z	Terminal-Phase Elimination Rate Constant
ZTI-01	Intravenous Fosfomycin Disodium

1. **PREFACE**

The Statistical Analysis Plan (SAP) for "A Phase 1 Safety and Intrapulmonary Pharmacokinetics Study of ZTI-01 (Intravenous Fosfomycin Disodium) in Healthy Adult Subjects" (DMID Protocol 16-0058) describes and expands upon the statistical information presented in the protocol.

This document describes all planned analyses and provides reasons and justifications for these analyses. It also includes sample tables, listings, and figures planned for the final analyses. Regarding the final analyses and Clinical Study Report (CSR), this SAP follows the International Conference on Harmonisation of Technical Requirements for Registration of Pharmaceuticals for Human Use (ICH) Guidelines, as indicated in Topic E3 (Structure and Content of Clinical Study Reports), and more generally is consistent with Topic E8 (General Considerations for Clinical Trials) and Topic E9 (Statistical Principles for Clinical Trials). The structure and content of the SAP provides sufficient detail to meet the requirements identified by the FDA and ICH, while all work planned and reported for this SAP will follow internationally accepted guidelines published by the American Statistical Association and the Royal Statistical Society for statistical practice.

Any deviation from this SAP will be described and justified in protocol amendments and/or in the CSR, as appropriate. The reader of this SAP is encouraged to also review the study protocol for details on conduct of the study and the operational aspects of clinical assessments.

2. INTRODUCTION

This is a Phase 1, open-label, multiple-dose trial conducted at a single center. The treatment period will consist of three 6 g doses of ZTI-01 as a 1 h IV infusion. A total of 30 enrolled subjects will be randomized. Six additional enrolled subjects will act as alternates. An evaluable subject is defined as a subject who receives all doses of ZTI-01, undergoes bronchoalveolar lavage (BAL) at the randomized sampling timepoint with BAL return volume adequate for testing, and undergoes at least the one blood sampling timepoint that is concurrent with the assigned BAL sampling timepoint, with blood sampling volume that is adequate for testing.

